9. DATA HANDLING AND RECORD KEEPING

Data will be collected on paper by study coordinators and transcribed into a RedCap database, which will be maintained at the Uof C. Data will be managed by the PI and study coordinators, and only the study team will have access to the data. All patient-specific identifiers will be kept separate from the primary research database. The research database will be organized by a unique patient code.

10. STUDY MONITORING, AUDITING AND INSPECTING

All periprocedural complications and adverse events will be reviewed by the PI at study midpoint to ensure there is no significant difference in event rate between the study groups. Should there be significant differences, or if there should be a high overall event-rate out-of-line with the procedural norm for AF, the study will be halted.

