1. INTRODUCTION

A. BACKGROUND AND RATIONALE

New-onset postoperative atrial fibrillation (POAF) commonly complicates cardiac surgery, affecting between 20 and 50% of patients,¹ with an even higher risk for patients undergoing combined coronary artery bypass graft (CABG) and/or valve replacement procedures.^{2,3} The spectrum of POAF varies from self-limited episodes to persistent AF requiring antiarrhythmic drug therapy (AAD) and cardioversion.

Overall, POAF portends significantly worse clinical outcomes, including an up to four-fold increased risk of stroke and doubling of both all-cause 30-day and 6 month mortality.⁴ In addition, POAF is independently associated with prolonged intensive care unit (ICU) stays, longer overall duration of hospitalization (extending length-of-stay by 2 to 5 days), and significantly increased costs by \$10,000-20,000, even during the index hospitalization.^{4,5} POAF usually occurs between 2 and 4 days after surgery, with a peak incidence on postoperative day 2.⁶ The pathogenesis of POAF in the cardiac surgical setting remains poorly understood, although there is data to suggest that autonomic imbalance during the post-operative period may play a key role for some patients.¹

Peripheral vagal nerve stimulation can alter central parasympathetic cardiac inputs, leading to reduced heart rate along with reduced dispersion of atrial effective refractory periods (AERPs), lowering the risk of AF.^{7,8} While direct vagal nerve stimulation has an established role in the treatment of intractable epilepsy and treatment-resistant depression,^{9,10} its application for POAF has been limited due to its invasive nature and increased risks.

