6. STATISTICAL PLAN AND CONSIDERATIONS

Primary Outcome:

1. Time to the first episode of AF >30 seconds during inpatient admission or within 14-day monitoring period

- a. In hospital: full-disclosure telemetry
- b. Time to AF will be assessed by physicians blinded to randomization
- 2. Extended hospitalization of >5 days

Secondary Outcomes:

- 1. Overall AF burden, as assessed by 2 week monitor (CardioNet or Zio Patch) upon discharge
- 2. Inflammatory markers: C-reactive protein (ordered if clinically indicated)
- 3. Actionable AF: antiarrhythmic use (including rate-control meds), CDV, anticoagulation, use of inotropes for BP support during AF
- 4. Stroke or transient ischemic attack (TIA)
- 5. All cause of mortality

Sample size estimation:

Assuming a two-armed study with composite endpoint of occurrence of AF or >5 days hospitalization, whereby the treatment group will have 50% likelihood of the event occurring and a control group will have 20% likelihood of the event occurring, as well as a 10% dropout rate, we will be able to detect differences in 80 patients (40 in each arm). Under these assumptions and using two-sided Z-Test with unpooled variance to compare the changes between these two groups, we will have 80% power ($\alpha=0.05$) to detect a difference between the group proportions of 0.30. PASS software Version 15 (NCSS, LLC, Kaysville, UT) was used to calculate the statistical power.

Statistical methods:

Patients will be studied based on the randomization allocation. Patients who refuse to continue with study treatment (i.e. they refuse to wear ear clip) during time of therapy will be analyzed as intention-to-treat per allocation group. Fisher's exact or the Chi-Square test will be used for categorical variables, and continuous parameters will be compared by the two-tailed unpaired Student's t test and the F test for analysis of variance (ANOVA), as needed. Kaplan-Meier method will be used for computing the event free survival curves. Each strategy will be compared within this cohort of patients for its impact on percent incidence of POAF and length of stay. Multiple logistic regression and multiple regressions using the Cox proportional hazards model will be performed to determine the independent association of each of the demographic variables with clinical outcome.

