8. SAFETY AND ADVERSE EVENTS

Safety:

As noted above, periprocedural complications will be logged with respect to procedure, system-related, and lead-related events. All complications will be independently reviewed at the midpoint by the primary investigator (PI). Should there be a trend towards increased complication risk, the study will be halted.

Adverse Events:

As noted above, all adverse events associated with devices will be monitored periprocedurally and continuously through the study. The PI will independently review all events after randomization of 20 subjects in order to make a determination for continuance.

Adverse Effect Documentation:

1. Sinus bradycardia or AVB after stimulation
2. Discomfort or possible skin abrasion due to tragus stimulation
3. Major organ-system failure
4. Death

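### Sections 8 and 10 give conflicting mandatory halting conditions for the same midpoint review, and Section 10 as worded would also halt for a significant difference in favour of LLTS

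*Combined protocol and SAP*

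**What the plan says.** Section 10 (Study Monitoring, Auditing and Inspecting) sets the task: "All periprocedural complications and adverse events will be reviewed by the PI at study midpoint", with the aim "to ensure there is no significant difference in event rate between the study groups". The consequence is a mandatory halt: "Should there be significant differences, or if there should be a high overall event-rate out-of-line with the procedural norm for AF, the study will be" … The section does not say which arm must do worse, which test is used, at what level, or which events are compared.

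Section 8 (Safety and Adverse Events) also has the PI review complications at the midpoint, but with another condition: "Should there be a trend towards increased complication risk, the study will be halted". It logs complications by procedure, system and lead, speaks of adverse events linked to the devices, and lists four adverse effects: sinus bradycardia or AV block, discomfort or abrasion, major organ-system failure, and death. It adds a PI review of all events once 20 subjects are randomized, to decide on continuing.

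The primary safety endpoint (end of Section 2) covers pain and tragus abrasion or bruising. Section 6 makes AF and a stay over 5 days primary outcomes, and stroke/TIA and all-cause mortality secondary outcomes. Its sample size rests on a single comparison: "we will have 80% power ($\alpha=0.05$) to detect a difference between the group proportions of 0.30".

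**The concern.** A safety rule normally looks for harm on the experimental arm. Section 10's difference clause has no direction, so a PI who follows it literally must stop the trial when sham does significantly worse. Section 8 would not stop the trial on that result. Conversely, a non-significant drift towards more complications on LLTS halts under Section 8 but not under Section 10's difference clause. The same data can therefore give opposite instructions, and someone who has already seen the between-arm results would have to choose between them.

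The undefined event set adds to this. If efficacy-type events entered the comparison, the safety review would become an unplanned efficacy look. It could end the trial at half its size, with no control of the error rate and with an effect estimate inflated by stopping on a significant result.

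**Working it through.** **1. The two rules side by side**

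| | Section 8 | Section 10 |
|---|---|---|
| Direction | increased risk only | none stated |
| Threshold | a trend, undefined | significant, with no test or alpha |
| Events | procedure-, system- and lead-related complications; device-associated adverse events; four listed effects | all periprocedural complications and adverse events |
| Timing | midpoint, plus a review after 20 randomized | midpoint |
| Consequence | mandatory halt | mandatory halt |

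The midpoint of 80 is 80/2 = 40, so the 20-subject review is a different time point. No halting criterion is attached to it. Section 10 also has a second trigger, a high overall rate judged against a procedural norm for AF. It gives no value for that norm, and the phrase is unclear.

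**2. The plan's sample size**

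Inputs from Section 6: 50% v 20%, two-sided alpha 0.05, 80% power, unpooled Z-test, 10% dropout.

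n per arm = (1.960 + 0.842)² × (0.5×0.5 + 0.2×0.8) / 0.30² = 35.76, rounded up to 36. Then 36/0.9 = 40 per arm, 80 in total. The stated figure reproduces (power at 36 per arm is 80.3%). It is a fixed design with one analysis and no allowance for an earlier stop.

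**3. Chance of a significant midpoint difference favouring LLTS, if AF-type events were counted**

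Assumptions: midpoint of 20 per arm (1:1 allocation); level 0.05 two-sided, borrowed from Section 6; Fisher or uncorrected chi-square, the tests Section 6 names for categorical data; lower rate on LLTS. Section 6 prints treatment at 50% and control at 20%. I take these as transposed, in line with the hypothesis in Section 1.B; the sample size is the same either way.

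With x events on sham and y on LLTS, the probability is the sum of Bin(x; n, p_sham) × Bin(y; n, p_LLTS) over all pairs with x > y and p < 0.05.

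| n per arm | Rates sham v LLTS | Fisher | Chi-square |
|---|---|---|---|
| 20 | 50% v 20% | 40.9% | 53.1% |
| 18 (10% dropout) | 50% v 20% | 35.9% | 49.8% |
| 20 | 35% v 20% (assumed) | 11.4% | 18.9% |
| 10 (20-subject review) | 50% v 20% | 13.2% | 25.4% |

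At 20 per arm and 50% v 20%, the chance of a significant excess on LLTS is below 0.01%.

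**4. Effect on completing the trial, under the same condition**

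In 200,000 simulated trials at 50% v 20% with a final unpooled Z-test, the chance of reaching the end with a significant result falls from 82–83% to 42% (Fisher halt) or 32% (chi-square halt) with 20 then 40 per arm. With 18 then 36 per arm it falls from 80% to 45% or 33%. A rule that halts only for a significant excess on LLTS leaves these chances unchanged.

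**5. If AF is not counted**

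For an event with the same true rate in both arms (20%, 35% or 50%), one comparison at 20 per arm significantly favours LLTS 1.0–1.3% of the time by Fisher and 2.1–2.6% by chi-square. Stroke/TIA alone, at assumed rates from 4% v 1% to 10% v 2% (not in the documents), gives 0.1–3% by Fisher and 0.6–9% by chi-square.

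**6. The undefined trend**

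If Section 8's trend were read as any numerical excess on LLTS, equal true rates of 10%, 20% or 30% at 20 per arm would show one 39%, 42% or 43% of the time. Direction without a threshold is therefore not enough.

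**The case against.** The strongest reply is that the events under review are narrow. Sections 2 and 8 point to device- and procedure-related events, and AF and stroke/TIA are in neither list. Section 1.A does say "New-onset postoperative atrial fibrillation (POAF) commonly complicates cardiac surgery, affecting between 20 and 50% of patients", but that is background prose and not a safety definition. The reference to AF in Section 10 belongs to the overall-rate clause, not the difference clause. Section 8's directional wording also suggests that harm is what was meant. Finally, the 50% and 20% are rates for AF or a stay over 5 days. A long stay is nowhere called an adverse event, and no AF-only difference is given.

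Most of this stands. A reader might infer that an effective LLTS would stop its own trial about half the time. The documents do not support that: it needs AF-type events to be counted, which no section states, and it applies composite rates to them. Stroke/TIA adds little in any case. Death is the only outcome that is explicitly both a listed adverse effect and an efficacy outcome.

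The reply does not remove the conflict. Section 10 describes its events more broadly than Section 8 and is not tied to Section 8's list. Section 8's direction does not carry over either: each section ends in its own mandatory halt, and an excess on sham would trigger one and not the other.

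**Conclusion.** The point holds as a contradiction between two mandatory halting conditions that differ on direction, threshold, event scope and timing. Section 10's wording, taken literally, includes a halt for a significant difference favouring LLTS. That much rests on the text alone.

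The size of the risk is conditional. It is about 41–53% at the plan's composite rates and 11–19% at 35% v 20%, given 20 per arm, a two-sided 0.05 test, the lower rate on LLTS and AF-type events counted. Without AF it is a few per cent or less per comparison for events with equal rates in the two arms. Because the documents do not settle the event set, neither figure can be called the trial's actual halt probability. The matter is worth correcting before the review takes place, since the choice would otherwise be made with the arm comparison in view.

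**What to change.** Reconcile Sections 8 and 10 into one halting condition, stated once and cross-referenced, with a single direction, threshold, event set and set of review times. In doing so:

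- say whether the 20-subject review is additional to the midpoint and what criterion applies there;
- clarify or remove the comparison with a procedural norm for AF;
- state whether primary-outcome events (AF, stay over 5 days) are counted, and how death is treated given its double role;
- state that the midpoint review is a safety review with no efficacy comparison, so that a difference favouring LLTS is not in itself a trigger.

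The harm threshold, and how an excess of AF on LLTS would be handled, are for the sponsor to decide; this review proposes neither.

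The cost is a few sentences, with no extra patients, staff or data. The small downside is that the trial could not stop at the midpoint for apparent benefit, a stop for which the sample size made no provision.

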11. FINANCIAL CONSIDERATIONS

No renumeration will be provided to subjects.

12. ETHICAL CONSIDERATIONS

No specific ethical considerations are identified in relation to this study.

13. CONFLICT OF INTEREST

This is an internally funded study with no external support.

15. APPENDIXES

A. FIGURES

Figure 1: Parasymp Device

Figure 2: Electrode attached to tragus

B. J AM COLL CARDIOL 2015;65:867–75

 Low-level
transcutaneous stimu

C. SCHEDULE OF EVENTS (SCHEMA)

	Screening	Surgery (Day 0)	Post-Op Days 1-2	Day of Discharge	Follow-Up Visit (2 weeks to 1 month after discharge)
Medical Records Review	X				X
Clinical Evaluation (Physical Exam, Vital Signs, Medication Review)	X	X	X	X	X
Electrocardiogram	X			X	
Echocardiogram	X ^a				X ^a
Urine Pregnancy Test	X ^b				
NYHA Functional Class Determination	X				
Randomization	X ^c				
LLTS or Sham Application		X ^d	X ^e		
C-Reactive Protein Blood Test		X ^f	X ^f		
Event Monitor (i.e. Zio Patch or Cardionet Monitor)				X ^g	X
Adverse Events		X	X	X	X

^a Results from records review, if available

^b Only for women of childbearing potential

^c Pre-procedure to facilitate planning of procedure

^d Immediately after surgery

^e Continuous for 48 hours

^f If clinically indicated

^g Pre-discharge if discharged on a weekday; arrangement for mailing or pick-up for patients discharged on a weekend day
